21 PUBLICATION POLICY

The first author of the primary publications will be [name], CCI and chairman of the Steering Committee of the BIOSync CLS trial. [name] will be responsible for the preparation of the final study report and of the manuscript of the main paper which must be approved by the Steering Committee before submission for publication

The authors of the primary publication will be 10 investigators (or more, depending on the journal requirements) with the highest scores. A minimum of 5 members of the Steering Committee is warranted. All the members of the Steering Committee will always be cited in any publication of study results.

Each Investigator will receive:

- 1 point for each enrolled subject
- 1 point for each enrolled subject with complete and compliant data set (by source data verification)
- +0.25 points for each compliant and fully reported scheduled in-hospital follow-up
- -0.25 points for each unreported or incompliant (e.g., out of window) scheduled follow-up visit
- -1 point for each underreported or delayed reported Serious Adverse Event, and (Serious) Adverse Device Effect.

The study design may be submitted for publication and the authors of this publication will be the members of the SC. Case reports cannot be submitted for publication by the investigators before the paper on the study design has been published.

Publication of sub-analysis will be submitted after the first main publication and the proposing center will have 2 or more authors. Sub-analysis must be approved by the Steering Committee.

3.1 Objectives

The study has the primary objective of comparing time to first syncopal recurrence between

- · active group (CLS): CLS in addition to DDD pacing mode; and
- control group (CTL): sensing only, ODO mode.

Definition. According to the 2018 ESC guidelines¹, a syncopal recurrence is defined as a transient complete loss of consciousness characterized by rapid onset, short duration, and spontaneous complete recovery.

The Secondary endpoint will be the time to the first recurrence of pre-syncope or syncope, whichever comes first, compared between the study groups during follow-up

Definition. Pre-syncope is defined as any of the various signs and symptoms which are recognized by the patients as premonitory of imminent syncope but not followed by syncope.

3.2 Primary hypotheses

Null: the 2-year survival rate of syncopal recurrence in the treatment arm (S_{CLS}) is equal to the 2-year survival rate of the control arm (S_{CTL}), assuming an exponential distribution with proportional hazard rates.

 H_0 : $S_{CLS}(t=2 \text{ years}) = S_{CTL}(t=2 \text{ years})$

Alternative: the 2-year survival rate of syncopal recurrence in the treatment arm is different from the 2-year survival rate of the control arm.

 H_1 : $S_{CLS}(t=2 \text{ years}) \neq S_{CTL}(t=2 \text{ years})$

[figure not shown]
3.3 Secondary hypotheses

Null: the 2-year survival rate to the combined event of pre-syncope or syncope, $\Sigma(t)$, is equal in both study groups

 H_0 : $\Sigma_{CLS}(t=2 \text{ years}) = \Sigma_{CTL}(t=2 \text{ years})$

Alternative: the 2-year survival rate to the combined event of pre-syncope or syncope is different in the two study groups.

 H_1 : $\Sigma_{CLS}(t=2 \text{ years}) \neq \Sigma_{CTL}(t=2 \text{ years})$

3 Investigation plan

The study is a prospective, multi-center, double-blinded, randomized, intention-to-treat, placebo-controlled study.

Patients will be randomized to the active group or to placebo immediately after their enrolment and before any subsequent study-related procedure.

- Active group: before post-implant hospital discharge, IPG will programmed in a dualchamber DDD pacing mode with the CLS function ON.
- Control group: before post-implant hospital discharge, pacing will be programmed in the ODO mode.

Randomization ratio will be 1:1, therefore the randomization procedure will ensure that each individual patient will have (approximately) 50% chance to be assigned to the active group or to the control.

Patient selection adheres to the class IIb indication for cardiac pacing of the guidelines of the European Society of Cardiology¹.

[figure not shown]
4.2 Inclusion criteria

Patients affected by clinical diagnosis of reflex (neurally-mediated) syncope who meet all the following criteria:

- age ≥40 years
- significant limitation of social and working life due to unpredictable frequent syncope recurrences, ≥2 of which within the last year.
- type 2B cardio-inhibitory response (VASIS classification) during TT performed according to the 'Italian protocol'.(7, 17)
- alternative therapies have failed or were not feasible.
- exclusion of other possible competitive causes of syncope.

4.3 Exclusion criteria

- Any classified indication to pacemaker different from reflex syncope with positive Tilt Test response
- Any classified indication implantable defibrillator (ICD), cardiac resynchronization therapy (CRT), according to current guidelines
- Any cardiac dysfunctions likely leading to loss of consciousness:
 - o overt heart failure;
 - o ejection fraction (LVEF) <40% (Echo-assessed within 3-month prior to study participation);
 - o myocardial infarction;
 - o diagnosis of hypertrophic or dilated cardiomyopathy;
 - o clinically significant valvular disease:
 - o sinus bradycardia <50 bpm or sinoatrial block;
 - o Mobitz I second degree atrioventricular block;
 - o Mobitz II second or third-degree atrioventricular block;
 - o bundle-branch block;

- o rapid paroxysmal supraventricular tachycardia or ventricular tachycardia;
- o pre-excited QRS complexes;
- o prolonged QT interval;
- o Brugada syndrome;
- o arrhythmogenic right ventricular cardiomyopathy;
- · Symptomatic orthostatic hypotension diagnosed by standing BP measurement;
- Nonsyncopal loss of consciousness (eg, epilepsy, psychiatric, metabolic, drop-attack, cerebral transient ischemic attack, intoxication, cataplexy).
- Symptomatic cardio-inhibitory carotid sinus hypersensitivity.

4.4 Study procedures

At enrolment, patients will receive anonymous syncope and pre-syncope assessment questionnaires to be self-administered upon each primary and secondary endpoint ever experienced and mailed (by ordinary mail) to an external CRO every 3 months after discharge b, using anonymous pre-paid and pre-addressed envelops.

Patients will be also visited in hospital at 12-, and 24-months. More frequent scheduled visits are optional and can be performed according to the site clinical practice. However, any scheduled or unscheduled in-hospital visit must be documented in the appropriate eCRF. Optionally, a 1-month $(\pm 14 \text{ days})$ in-hospital visit may be performed to repeat the TT.

4 Determination of sample size

The study sample size calculation is based on the minimum relative difference in the 2-year incidence of syncopal recurrences as compared with placebo (pacemaker OFF).

The 2-year incidence of the primary endpoint in the control group will be assumed equal to the incidence observed in the control arm of the ISSUE 3 trial: ² this was reported as high as 57%. The ISSUE 3 trial was considered as it selected a large population, had very similar inclusion/exclusion criteria, was recently published.

The BIOSync CLS study is designed to detect a 40% relative reduction of the 2-years incidence of syncopal recurrences (from 57% to 34%) with a statistical Type I and II errors of 0.05 (bilateral) and 0.20, respectively.

Further assumptions:

- Exponential distribution of times to first recurrence
- Accrual time: 2 years
- Total study time: 4 years
- Randomization ratio: 1:1
- Loss incidence: 10% (both arms)

With these assumptions a sample size of 62 patients per study arm (124 in total) is required. This estimate must be further increased by 2%, due to the slight power loss induced by the interim analyses.

In summary, 128 subjects (64 per study arm) are necessary to reach the study primary objective with the required power.

The required number of primary endpoint events is 62, as calculated with the formula:

events =
$$\frac{\left(z_{\alpha/2} + z_{\beta}\right)^{2}}{0.25 \log(HR)}$$

where $z_{\alpha/2}$ and z_{β} are the standard normal percentiles (α =0.05, β =0.20), HR is the expected hazard ratio. A HR of about 0.49 was calculated assuming an exponential model of the survival functions with proportional hazard rates.

5 Database cleaning

Data entered into the Clinical Data Management System (CDMS) is checked with programmed quality checks: input errors, discrepancies, missing data, and out-of-range values are resolved automatically (CDMS) or manually (clinical monitor, data manager) by means of data queries. The CDMS supports detailed tracking of the query process. Corrections to eCRF can only be done by the designated site personnel and need to be signed by the investigator. All changes are automatically recorded in the system's audit-trail.

6 Statistical methods

7.1 General methodology

Continuous variables will be summarized using tables of descriptive statistics: number of patients with recorded observations, mean, standard deviation, median, interquartile boundaries, minimum and maximum. Categorical variables will be summarized using counts and percentages. Descriptive statistics will be presented by randomization group.

Comparison of continuous parameters between two groups will be performed using T-test or Wilcoxon Man-Whitney U test, after testing for normality with the Shapiro-Wilk test. Categorical variables will be compared using the Chi-Square or Fisher exact test, as appropriate.

For the analysis of the primary and the secondary endpoint the Kaplan-Meier plots will be generated and the estimated survival functions of the study groups tested with the two- sided log-rank test. Dependence of survival on major baseline predictors will be evaluated with proportional hazard Cox models. Proportionality of hazards will be tested with the Schoenfeld Residuals test. Hazard ratios and relative 95% confidence intervals for each predictor will be calculated, respectively. Data will be censored at the date of last patient contact. The ITT principle will be applied.

All applicable statistical tests will be 2-sided and will be performed using a 5% significance level. All confidence intervals presented will be 95% and two-sided. Statistical calculations will be carried out by using STATA $11.1 \, \text{@}$, SAS $9.3 \, \text{@}$ or R.

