8.8.6 Point of enrolment and study termination

A subject is considered enrolled in the BIOSync CLS Study upon the signature of the Informed Consent Form.

Patients will terminate their study participation at the 24-month in-hospital follow-up or at the assessment of a primary endpoint event occurrence, whichever comes first.

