11 STATISTICAL CONSIDERATIONS

11.1 Statistical design, method and analytical procedures

Standard summary statistics will be calculated for all patients and study outcome variables. Categorical data will be summarized via distributions of absolute and relative frequencies. For all relevant parameters 95% confidence intervals will be calculated.

For the analysis of the primary endpoint and the secondary endpoint the Kaplan-Meier plots will be generated and the estimated survival functions of the study groups tested with the two-sided log-rank test. Dependence of survival on major baseline predictors will be studied with proportional hazard Cox models. Hazard ratios and relative 95% confidence intervals for each predictor will be calculated, respectively. Data will be censored at the date of last patient contact. The ITT principle will be applied.

Statistical calculations will be carried out by using STATA 11.1 ®, SAS 9.3 © or R.

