11.2.1 Required number of primary endpoint events

The required number of primary endpoint events is 62, as calculated with the formula:

$$events = \frac{(z_{\alpha/2} + z_{\beta})^2}{0.25 \log(HR)}$$

where $z_{\alpha/2}$ and z_{β} are the standard normal percentiles ($\alpha=0.05$, $\beta=0.20$), HR is the expected hazard ratio. A HR of about 0.49 was calculated assuming an exponential model of the survival functions with proportional hazard rates.

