7.7 Clinical Investigation Plan (CIP) deviations

All CIP deviations will be classified with details of the type of deviation and the full-list will be provided in the Clinical Investigational Report (CIR).

The number (and percentage) of patients with major and minor protocol deviations will be summarized by randomization group.

A post-hoc per-protocol analysis according to the existing data gathered could be run after the evaluation of the provided deviations.

Page 14/14

References

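### Adverse events and deviations are reported without regard to follow-up time, although leaving the study at the first assessed syncope is expected to give the CLS arm about 11–21% more follow-up than ODO

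*SAP*

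**What the plan says.** SAP 7.1 gives the general rule for categorical data: "Categorical variables will be summarized using counts and percentages. Descriptive statistics will be presented by randomization group". The same section allows chi-square or Fisher tests between groups. Protocol 11.1 is similar ("Categorical data will be summarized via distributions of absolute and relative frequencies") but does not mention arms. SAP 7.7 is specific: "The number (and percentage) of patients with major and minor protocol deviations will be summarized by randomization group". It names no test.

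The primary and secondary endpoints are handled differently. SAP 7.1 and the code in SAP 7.5 use Kaplan-Meier curves, the log-rank test and Cox models, with censoring at last contact.

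The SAP has no adverse-event section. Its variable lists cover baseline and endpoint variables only. Neither document mentions patient-years, an exposure denominator or time to first adverse event.

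Under Protocol 8.8.6 a patient leaves at the 24-month visit "or at the assessment of a primary endpoint event occurrence, whichever comes first". Protocol 20.3 then follows only serious events that are still ongoing: six weeks in general, and up to six months for device-related serious effects. No collection of new events after exit is described.

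**The concern.** Time at risk for an adverse event or a deviation is cut short by the primary endpoint. If CLS works, ODO patients leave sooner, so the same underlying event rate produces a smaller percentage of ODO patients with an event. A crude percentage then mixes the event rate with the treatment effect on syncope.

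This matters because permanent ODO programming is an off-label use with its own risk analysis (Protocol 4.5, 6.2.1 and 6.2.3). A reader of the final report will want to compare safety between the arms. Percentages without a time denominator would tilt that comparison towards ODO. They would tilt the deviation comparison the same way wherever deviations build up over follow-up.

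**Working it through.** **Inputs from the documents** (Protocol 11.2 and 11.2.1; SAP, Determination of sample size)
- Two-year recurrence: 57% ODO, 34% CLS.
- "Exponential distribution of times to first recurrence".
- 64 patients per arm, at most 2 years each (Protocol 8.8.7).
- Loss of 10% in both arms. No time unit is given; I take it as 10% over 2 years.

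**Assumptions not in the documents**
- Delay from syncope to assessment: 1.5, 3 or 6 months. Questionnaires are mailed quarterly (Protocol 8.3.3).
- Constant first adverse-event rate r, equal in both arms: 0.05 to 0.40 per patient-year.

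**Step 1: reproduce the plan's figures.** The hazards are λ = −ln(1 − p)/2:
- ODO: −ln(0.43)/2 = 0.4220 per year.
- CLS: −ln(0.66)/2 = 0.2078 per year.

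The ratio is 0.492, which agrees with the protocol: "A HR of about 0.49 was calculated assuming an exponential model of the survival functions with proportional hazard rates". With HR = 0.49, (1.960 + 0.842)² / (0.25 × [ln 0.49]²) = 61.7, hence the stated 62 events. (The printed formula omits the square on the logarithm; 62 needs it.) The inputs are therefore the ones that the plan used.

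**Step 2: mean follow-up per patient.** If exit is at the syncope, the mean is (1 − e^(−2λ))/λ. If exit comes d years after the syncope, it is d + (1 − e^(−(2−d)λ))/λ.

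| Exit | ODO (years) | CLS (years) | CLS/ODO |
|---|---|---|---|
| At the syncope | 1.351 | 1.637 | 1.21 |
| At the syncope, with 10% loss | 1.291 | 1.559 | 1.21 |
| Assessed 1.5 months later | 1.421 | 1.678 | 1.18 |
| Assessed 3 months later | 1.487 | 1.717 | 1.15 |
| Assessed 6 months later | 1.611 | 1.789 | 1.11 |
| Any of these, if HR = 1 | equal | equal | 1.00 |

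At 64 per arm the first row is 86.4 against 104.7 patient-years.

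**Step 3: effect on crude percentages.** With exit at the syncope, the expected percentage with at least one event is r/(r + λ) × (1 − e^(−2(r + λ))). For r = 0.10:
- ODO: 0.10/0.5220 × (1 − e^(−1.0440)) = 12.4%.
- CLS: 0.10/0.3078 × (1 − e^(−0.6155)) = 14.9%.

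| Assumed r per patient-year | ODO | CLS | Gap (points) |
|---|---|---|---|
| 0.05 | 6.5% | 7.8% | 1.3 |
| 0.10 | 12.4% | 14.9% | 2.5 |
| 0.20 | 22.9% | 27.3% | 4.5 |
| 0.40 | 39.3% | 46.3% | 7.0 |

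The true rates are equal in every row. With a delay to assessment the gaps are narrower, because the follow-up times lie closer together.

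**Step 4: a deviation that needs follow-up.** On the plan's rates 43% of ODO and 66% of CLS patients reach month 24 free of syncope. About 0.66/0.43 = 1.5 times as many CLS patients can therefore miss the 24-month visit or attend outside its window.

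**The case against.** The strongest reply has five parts.

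- **The plan does not reduce all outcomes to crude percentages.** Correct. A reader of the general rule alone might infer that it does, but the two defined endpoints use censored methods in the same section.
- **No adverse-event table is planned, so crude adverse-event percentages are an inference.** Also correct. The documents do not commit to such percentages. They leave the method and the denominator unstated, with the general rule as the only default. For deviations the percentage is explicit.
- **21% is the upper end.** It assumes exit at the syncope, whereas the protocol ends participation at assessment. Stopping at an interim analysis would shorten follow-up too: with follow-up cut at 12 months the ratio is 0.903/0.816 = 1.11. The range must be given, and it reaches 1.00 if CLS has no effect.
- **Nothing about ODO is hidden.** A reader might infer that ODO events are undercounted. The documents do not support that. Observed counts are right, ODO must be switched off at study exit (Protocol 9.5.5), and adverse events accompanying a recurrence remain reportable (Protocol 9.6, Table 4). Only the percentage is lowered, relative to equal follow-up. Many complications in Protocol Table 1 concern venous access, leads or the pocket; those arising around implant precede most recurrences.
- **The distortion is small beside sampling error.** At r = 0.10 the gap is 2.5 points, against a standard error of √(0.124 × 0.876/64 + 0.149 × 0.851/64) ≈ 6 points. True, but it is a systematic shift in a known direction, and it is cheap to remove.

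One further caution stands. Rates per patient-year do not suit deviations that can occur only once, such as consent or eligibility errors.

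**Conclusion.** The point holds for adverse events after the implant period and for deviations that accrue over follow-up. Under the planning assumptions the CLS arm is expected to have about 11–21% more follow-up, depending on the delay from syncope to assessment. At equal true rates the ODO percentage would fall about 1 to 7 points below the CLS percentage for assumed rates of 0.05 to 0.40 per patient-year with exit at the syncope.

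These sizes rest on the plan's 57% and 34%, exponential recurrence times, and event rates and delays that I have assumed. The primary and secondary inference, the type I error and the pass criterion are not affected. This is a weakness in safety and conduct reporting that should be corrected. It is not a flaw in the efficacy analysis.

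**What to change.** **SAP 7.1**
- Report patient-years of follow-up by arm, counted to study exit. The derived primary-endpoint time in SAP 7.5 stops at the syncope, so it is not the right denominator.
- Keep counts and percentages for all adverse events, and show peri-procedural events (implant to 30 days) separately as percentages.
- For later adverse events, serious events, serious device effects and crossovers, add events per 100 patient-years by arm with 95% confidence intervals.
- Add time to first serious adverse event, censored at study exit. State that censoring at an exit caused by syncope may be informative, especially for syncope-related serious events.

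**SAP 7.7**
- Add patient-year rates beside the percentages only for deviations that accrue over follow-up, such as missed or out-of-window visits.
- Leave one-off deviations (consent, eligibility, discharge programming) as percentages.

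The cost is a short paragraph, a few lines of code and one extra table. Adverse-event and termination forms exist (Protocol 8.4.1), but their fields are not shown, so the sponsor should confirm that onset and exit dates are recorded.

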11.3 Level of significance and the power of the study

Target study power: 80%

Significance level: 0.05 (bilateral)

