11.5 Pass/fail criteria

The clinical investigation is deemed to be passed if the alternative hypothesis of the primary endpoint is reached.

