11.6 Provision for interim analyses

Interim analyses will be performed at $t = 0.4$ and 0.7 of the required primary endpoint events or, equivalently, after 25 and 43 endpoint events will be collected.

The final analysis will be performed after the study database has been closed out.

In order to keep the overall type I error at the level of 0.05, two-sided, symmetric O'Brien-Fleming boundaries generated with the Lan-DeMets spending function approach to group-sequential testing will be assumed as early stopping rules for efficacy.

| | | | |
|---------------------|---------|---------|---------|
| t | 0.40 | 0.70 | 1.00 |
| No. endpoint events | 25 | 43 | 62 |
| Z_{up} | 3.3569 | 2.4445 | 2.0005 |
| Z_{low} | -3.3569 | -2.4445 | -2.0005 |
| p | 0.0008 | 0.015 | 0.05 |

Sequential boundaries using the Lan-DeMets method

[figure not shown]

Figure 2. Sequential boundaries during interim analyses. R Software version 3.1.0 (2014-04-10).

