11.7 Termination criteria

With a **sequential study design** the study will stop when a total of 62 primary endpoint events will be collected by the independent agency. The following stopping rules will be used.

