7.6 Interim analysis

Interim analyses will be performed at t=0.4 and 0.7 of the required primary endpoint events or, equivalently, after 25 and 43 endpoint events will be collected. The final analysis will be performed after the study database has been closed out. In order to keep the overall type I error at the level of 0.05, two-sided, symmetric O'Brien-Fleming boundaries generated with the Lan-DeMets spending function approach to group-sequential testing will be assumed as early stopping rules for efficacy.

t	0.40	0.70	1.00
No. endpoint events	25	43	62
Zup	3.3569	2.4445	2.0005
Z_{low}	-3.3569	-2.4445	-2.0005
р	0.0008	0.015	0.05

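### The printed final boundary (|Z| = 2.0005, nominal p = 0.0454) is correct and meant to govern, but SAP 7.1 does not exempt the primary log-rank test from its 5% level, and the boundary table shows an unlabelled 0.05 in the same column

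*SAP*

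**What the plan says.** Protocol 11.6 and SAP 7.6 carry the same table, with looks at 25, 43 and 62 events (t = 0.40, 0.70, 1.00). In the protocol the upper boundary row reads "Z_{up} | 3.3569 | 2.4445 | 2.0005" and the last row reads "p | 0.0008 | 0.015 | 0.05". Nothing in the available text defines p in that last row. The purpose of the boundaries is stated in SAP 7.6: "In order to keep the overall type I error at the level of 0.05, two-sided, symmetric O'Brien-Fleming boundaries", generated by Lan-DeMets spending. Both documents describe them as rules for stopping early for efficacy.

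SAP 7.1 specifies the primary analysis, with "the estimated survival functions of the study groups tested with the two- sided log-rank test". Its next paragraph adds "All applicable statistical tests will be 2-sided and will be performed using a 5% significance level". It neither exempts the primary test nor refers to SAP 7.6.

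Three other places bear on the threshold without settling it. Protocol 11.3 gives 0.05 two-sided and does not say whether this is the overall level or the level at the last look. Protocol 11.5 sets the pass criterion without a number: "The clinical investigation is deemed to be passed if the alternative hypothesis of the primary endpoint is reached". Protocol 11.7.1, step 5, refers the independent statistician to the SAP, which contains both 7.1 and 7.6.

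Protocol 11.2 and the SAP sample-size section both raise the sample size by 2% for the power lost through the interim analyses.

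**The concern.** |Z| = 2.0005 and p = 0.05 are different cut-offs, since two-sided p = 0.05 corresponds to |Z| = 1.96. Someone who applies SAP 7.1 as written, or who takes the last row of the table as the p-value to beat, would judge the final log-rank test at 0.05. The row invites this. At the first two looks its entries are almost the same as the nominal p-values, and only at the last look do the two quantities separate visibly.

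This is the decision rule for the primary endpoint. A final p between 0.0454 and 0.05 would fail against the printed Z and pass under the literal reading of SAP 7.1. Settling the question after such a p-value had been seen would be hard to defend.

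**Working it through.** **Inputs.** Overall two-sided alpha 0.05; t = 0.40, 0.70, 1.00; printed Z of 3.3569, 2.4445, 2.0005 (Protocol 11.6, SAP 7.6). HR 0.49, 62 events and 1:1 allocation (Protocol 11.2 and 11.2.1, SAP sample-size section).

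**Step 1: reproduce the plan's boundaries.** Use O'Brien-Fleming-type spending with 0.025 on each side. The cumulative two-sided alpha at t is 2 × 2 × [1 − Φ(2.2414/√t)], where 2.2414 is the upper 0.0125 normal point. Boundaries are solved by recursive numerical integration, and nominal p = 2 × [1 − Φ(Z)].

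| t | Z recomputed | Cumulative alpha spent | Nominal two-sided p | Printed p row |
|---|---|---|---|---|
| 0.40 | 3.3569 | 0.0008 | 0.0008 | 0.0008 |
| 0.70 | 2.4445 | 0.0148 | 0.0145 | 0.015 |
| 1.00 | 2.0005 | 0.0500 | 0.0454 | 0.05 |

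All three printed Z values are reproduced. The p row matches the cumulative alpha.

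**Step 2: overall type I error under each reading** (same integration, no treatment effect):
- printed Z at all three looks: 0.0500
- printed Z at the interims, p < 0.05 (|Z| ≥ 1.96) at the final look: 0.0542, or +0.42 percentage points
- the whole p row used as cut-offs (0.0008, 0.015, 0.05): 0.0544

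**Step 3: power.** The drift is |ln 0.49| × √(62/4) = 0.7133 × 3.937 = 2.808.
- one look only at 1.96: Φ(2.808 − 1.960) = 80.2%
- three looks with the printed boundaries: 79.6%
- three looks with 1.96 at the last: 80.7%

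The interim looks therefore cost power only if the final look uses 2.0005. With 1.96 at the end they would add power, and there would be no loss for a 2% increase to offset.

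**Step 4: chance of ending in the disputed range.** This is the difference between the two rules' rejection probabilities:
- no effect: 0.0542 − 0.0500 = 0.4%
- HR 0.49: 80.65% − 79.60% = 1.1%
- maximum: 1.5%, at a drift of about 2.0, or HR = exp(−2.0/3.937) ≈ 0.60

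At 62 events the observed HR at each cut-off is exp(−2.0005/3.937) = 0.602 and exp(−1.96/3.937) = 0.608.

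**Step 5: sensitivity to event counts.** 25/62 = 0.4032 and 43/62 = 0.6935, so the planned counts are not exactly 0.4 and 0.7. The same spending function at these fractions gives Z = 3.342, 2.4585, 1.9991 (nominal p 0.0008, 0.0140, 0.0456). Keeping the printed Z unchanged at these fractions gives an overall error of 0.0501.

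**The case against.** A reader might infer that the plan states two rival final thresholds and leaves the choice open, or that the table is wrong. The documents do not support either reading:
- The table prints a boundary at t = 1.00. Nothing can stop early there, so that entry can only be the final critical value, even though the text describes the boundaries as early stopping rules.
- The boundaries are introduced as the means of holding the overall error at 0.05. Step 2 shows that 2.0005 does this and 1.96 does not.
- The 2% increase in sample size makes sense only with the adjusted final boundary (step 3).
- A group-sequential test with overall alpha 0.05 is itself a 5% test, so SAP 7.1, as general methodology, can be read in harmony with SAP 7.6.
- The 0.05 in the p row is correct as cumulative alpha. Protocol Figure 2 is not shown, so a label there cannot be excluded.

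A reader might also see a serious gap in the lack of text on recalculating boundaries when event counts differ from plan. A footnote to Protocol 11.7.1 does allow for overshoot. But the spending-function approach already implies recalculation, and at the planned counts the difference is negligible (0.0501).

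These arguments establish what was intended. They do not remove the literal wording: SAP 7.1 sets its level for each test performed, directly after naming the primary log-rank test, and the table puts an undefined 0.05 in the final column.

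**Conclusion.** The concern holds as a point of wording with a small numerical consequence. The boundary is correct, identical in both documents and evidently meant to govern the final test. What is missing is an exemption for the primary test in SAP 7.1 and a label on the p row. Followed literally, the 5% level gives an overall two-sided type I error of 5.4% instead of the stated 5.0%. It changes the conclusion only if the final p lies between 0.0454 and 0.05, with probability 0.4% under no effect, 1.1% at HR 0.49 and at most 1.5%. It is worth correcting because it concerns the primary decision rule and costs almost nothing.

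These figures assume an approximately normal log-rank statistic, information proportional to events, looks at t = 0.40, 0.70 and 1.00, and a final analysis at 62 events.

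**What to change.** - **SAP 7.1:** state that the primary log-rank test is judged at every look, including the final one, against the SAP 7.6 boundary (final |Z| ≥ 2.0005, nominal two-sided p ≤ 0.0454), and that the 5% per-test level applies to the other tests.
- **Protocol 11.6 and SAP 7.6:** relabel the p row as cumulative two-sided alpha spent, and add a row of nominal two-sided p-values: 0.0008, 0.0145, 0.0454.
- **Optional:** note that the boundaries are recalculated from the same spending function at the actual event counts.

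Protocol 11.3 can stand as the overall alpha. The cost is wording, plus one short recalculation per look if the optional note is adopted. The final threshold is slightly stricter than 0.05: power at HR 0.49 with 62 events is 79.6% rather than 80.7%. The event target and the conduct of the trial do not change.
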